#### 2.11 STUDY DISCONTINUATION AND COMPLETION

#### 2.11.1 Definition End of Trial

End of Study (EOS) is defined as the last visit of the last subject, i.e. subject 24.

# 2.11.2 Criteria for temporary halt and early termination of the clinical trial

In accordance with CTR: Annex I D17p, dose escalation will be stopped (temporarily) when one of the following conditions applies:

- in case of an unacceptable tolerability profile based on the nature, frequency, and intensity of observed AEs, judged jointly by the investigator and the sponsor.
- if two or more subjects on active drug experience a serious adverse event (SAE) or severe AEs, which in the opinion of the PI or the Sponsor's medical representative is likely to be causally related to IMP.

If dose escalations are suspended because one or more of the above defined stopping criteria are met, the study team will review all available PK, safety, and tolerability data and may decide to unblind. Based on this review, it may be decided to repeat a dose level or, if observed changes are deemed to have occurred by chance (i.e., similar changes are observed in placebo-treated subjects), to proceed with further dose escalations.

If the reason(s) for temporary halt did not impact the risk-benefit ratio for subjects (Article 37 CTR), the EC shall be informed, and the study can be resumed. If the reason(s) for temporary halt impacted the risk-benefit ratio for subjects (Article 38 CTR), a substantial amendment shall be submitted to CCMO and EC. In such case, the trial will not be resumed until approval has been received.

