#### **Trial Design**

This is a randomized, double-blind, double dummy, placebo-controlled, two-way cross-over study to investigate the pharmacodynamic effects and adverse effects of morphine and nortriptyline in patients with chronic neuropathic pains.

Each study participant will receive the following study treatments:

- Morphine 3 mg IV + 7 mg IV + placebo
- Nortriptyline 75 mg orally + Morphine 3 mg IV + Morphine 7 mg IV

Protocol time Treatments	0h00m	2h00m	5h00m			
1	Placebo	Morphine 3 mg IV	Morphine 7 mg IV			
2	Nortriptyline 75mg	Morphine 3 mg IV	Morphine 7 mg IV			

In total, each subject will be exposed to two treatment options. Each treatment period will consist of one study visit to the clinical research unit. During this visit, arrival to the clinical research unit will be in afternoon of day before dosing (Day-1). In the morning of the next day (Day 1), subjects will receive the study treatment prior which and after which pharmacokinetic (PK) assessments and the pharmacodynamics (PD) will be performed. Subjects will be discharged in the afternoon of Day 2. Each study period will be followed by a wash-out period of at least 7 days and a final follow-up visit 7-14 days after the last dosing day.

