#### 2.7 STUDY TREATMENTS

#### 2.7.1 Investigational Medicinal Product(s) (IMP(s))

#### Name and description of the IMP

Nortriptyline

Nortriptyline 75 mg will be administered orally.

Morphine

Morphine hydrochloride (HCl) 3 mg and 7mg will be administered intravenously.

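### The halting rule in section 2.11.2 is worded for an ascending-dose trial, and its placebo test for chance cannot rule out a morphine effect, because both listed regimens contain morphine

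*Protocol*

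**What the plan says.** Protocol section 2.11.2 (Criteria for temporary halt and early termination of the clinical trial) has four parts.

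- **Action.** "dose escalation will be stopped (temporarily) when one of the following conditions applies".
- **Triggers.** One is a joint judgement by the investigator and the sponsor that tolerability is unacceptable. The other is a count, "if two or more subjects on active drug experience a serious adverse event (SAE) or severe AEs", where the event in the opinion of the principal investigator or the sponsor's "medical representative is likely to be causally related to IMP".
- **Review.** "the study team will review all available PK, safety, and tolerability data and may decide to unblind". Afterwards a dose level may be repeated or, "if observed changes are deemed to have occurred by chance (i.e., similar changes are observed in placebo-treated subjects), to proceed with further dose escalations".
- **Resumption.** If the reason for the halt did not affect risk-benefit, the ethics committee is informed and the study can resume. If it did, a substantial amendment is submitted. "In such case, the trial will not be resumed until approval has been received".

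The design stands elsewhere. The synopsis (Trial Design) lists two regimens: placebo with morphine 3 mg and 7 mg IV, and "Nortriptyline 75 mg orally + Morphine 3 mg IV + Morphine 7 mg IV". Section 2.7.1 repeats the list and names morphine as an IMP ("Morphine hydrochloride (HCl) 3 mg and 7mg will be administered intravenously"). It places the boluses at 2 h and 5 h in both arms. Table 3 in section 2.10.2 gives 24 subjects in one cohort.

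**The concern.** The rule presupposes a trial that steps up through dose levels and has subjects who receive placebo and nothing else. Neither fits the listed regimens. Three elements are affected: the action taken when a trigger is met, the options after review, and the test for calling an observation chance. The last matters most, because it supplies the reasoning the team is asked to use when deciding whether to continue.

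The exposure is foreseeable. Section 2.2.2 describes respiratory depression as the most serious and a very common side effect of morphine, and the synopsis says it is dose-dependent above 3 mg. If morphine causes events in both regimens, a criterion that treats similarity between regimens as evidence of chance points the wrong way. The protocol plans no data monitoring committee (2.12.10), no interim analysis (2.13.7) and no statistical termination criterion (2.13.8). The count in 2.11.2 is therefore its only numeric trigger at trial level.

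**Working it through.** Section 2.11.2 states no error rate or probability, so there is no figure to reproduce. The check sets the rule beside the design.

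**1. Which regimens exist.** Inputs: 24 subjects (2.5.2, Table 3) and two regimens each (synopsis, 2.7.1).

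- Planned subject-periods: 24 × 2 = 48, of which 24 are placebo + morphine and 24 nortriptyline + morphine.
- Morphine per period: 3 + 7 = 10 mg in both regimens.
- Periods with morphine: 24 + 24 = 48. Periods without morphine: 48 − 48 = 0.

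These counts are conditional, because other text conflicts with two regimens. Table 1 is headed for periods 1 to 4. Sections 2.5.2, 2.5.3 and 2.7.1 mention four occasions or periods. Table 3 gives four treatments, with placebo counted as one. The synopsis rationale and section 2.2.1 announce a comparison with each drug alone and with placebo. None of this defines a placebo-only regimen. Every treatment list shows the same two regimens, and section 2.13.6 plans a single contrast, the combination against morphine. The two-regimen reading is the better supported one.

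**2. The action.** The only rise in dose is the fixed step from 3 mg at 2 h to 7 mg at 5 h on the same day, identical in both regimens. Stopping escalation can mean at most withholding the second bolus. As written, it stops neither a subject's next period nor further enrolment. A halt of the trial has to be inferred from the section heading and the last paragraph.

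**3. The options after review.** Dose does not change between cohorts or periods, so repeating a level and escalating further have no clear counterpart.

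**4. The chance criterion.** There are two ways to read subjects treated with placebo.

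- *Placebo + morphine.* Both regimens carry the same morphine. A true morphine effect predicts similar events in both, so similarity cannot separate chance from that effect.
- *Drug-free placebo.* No such regimen is listed, so the criterion cannot be met for events after the first bolus.

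The comparison is sound for one purpose: 24 against 24 periods for what nortriptyline adds. For morphine, the available reference is within subject: pre-dose values and the 2 − 0 = 2 h before the first bolus in each period.

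**5. The count trigger.** Subjects on active drug may mean those on nortriptyline, which covers 24 of the 48 periods and ignores severe morphine events in the other 24. It may instead mean those on any IMP, which covers all 48 and leaves nobody as a placebo contrast after the first bolus. The text does not say which.

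**The case against.** The best defence is that this is leftover template wording with little practical effect. The 3 mg to 7 mg step is a kind of escalation that could be stopped. The heading and last paragraph show that a trial halt is intended. The count trigger requires a likely causal relation to IMP, and the team reviews all data, may unblind, and is not obliged to call anything chance. Section 2.11.3 requires interruption or discontinuation when dosing is against a subject's interest. Section 2.12.8 suspends the study when safety is jeopardised, section 2.12.9 covers urgent measures, and section 2.15.7 makes restart after a safety halt a substantial modification needing authorisation.

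Most of this stands and limits the harm. It does not make the criterion valid for morphine or give the operative sentence an action that fits the trial. The restart gates are also not wholly separate from the criterion. Which branch applies depends on whether benefit-risk was affected, and a finding of chance would bear on that; this last step is inference, not protocol text.

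Two stronger readings are tempting. A reader might infer that one severe event in each regimen both meets the trigger and supplies its own excuse. That requires the same subject-period to count as on active drug and as treated with placebo, whereas 2.11.2 uses the two terms as opposites. A reader might also infer that the rule would usually dismiss a real morphine effect. The documents give no rate of related severe or serious events, so no such frequency can be stated.

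**Conclusion.** The point holds as a defect in a stated safety rule. The escalation wording does not fit two fixed regimens. The placebo test is not valid for morphine-related events and is usable only for nortriptyline's added effect. The population for the count trigger is ambiguous.

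The size is a design fact, not a measure of harm: on the two-regimen reading, 48 of 48 planned periods contain morphine. If a placebo-only regimen were truly intended, the criterion would gain a reference group, but the escalation wording would still misfit.

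A reader might conclude that the trial has no halting provision. The documents do not support that: 2.11.2 implies a halt, and 2.12.8 and 2.15.7 provide for suspension and restart. The correction should be made, but the harm is possible rather than automatic.

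**What to change.** Reword section 2.11.2:

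- (a) State that further dosing and enrolment are temporarily halted when a trigger is met.
- (b) Delete the options to repeat a dose level and to escalate further.
- (c) Word the count trigger as two or more subjects who received any IMP, including morphine, in either regimen. Keep the severity and causality conditions.
- (d) Replace the placebo criterion with a review of events by actual regimen and by time relative to the 2 h and 5 h boluses. Use the between-regimen comparison only for nortriptyline's added effect, and state that similar events in both regimens do not rule out a morphine effect.
- (e) Let resumption follow the existing Article 37/38 paragraph.

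The cost is protocol wording in one section, with no extra patients or procedures. A small downside is that (c) may trigger a halt slightly more often.

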### 2.11.3 Discontinuation/withdrawal of individual subjects

Study drug interruption or discontinuation

Before trial medication is administered, changes in the subject health status including laboratory results if applicable, since the previous visit or previous dose in case of a multiple dose regimen, must be checked. The investigator must temporally interrupt or permanently discontinue the study drug if continued administration of the study drug is believed to be contrary to the best interests of the subject. The interruption or premature discontinuation of study drug might be triggered by an AE, a diagnostic or therapeutic procedure, an abnormal assessment (e.g., ECG or laboratory abnormalities), or for administrative reasons in particular withdrawal of the subject's consent. The reason for study drug interruption or premature discontinuation must be documented.

#### Subject withdrawal

Subjects have the right to withdraw from the study at any time for any reason. Should a subject decide to withdraw from the study, all efforts should be made to complete and report the observations, particularly the FU examinations, as thoroughly as possible.

#### Replacement policy

Subjects withdrawing, or being withdrawn, for reasons other than (possibly or probably related) AEs or any other tolerability issues with the treatment can be replaced at the discretion of the investigator. The rationale for replacement must be clearly documented in the source (e.g., note in Promasys, Filenotes, etc.)

## 2.11.4 Arrangements for subjects after their participation in the clinical trial ended

Not applicable.

#### 2.12 SAFETY REPORTING

#### 2.12.1 Definitions

### Adverse events (AEs)

Adverse events are defined as any untoward medical occurrence in a subject to whom a medicinal product is administered, and which does not necessarily have a causal relationship with this treatment.

The intensity/severity of clinical AEs is graded on a 3-point scale as defined below:

- Mild: discomfort noticed but no disruption of normal daily activity,
- Moderate: discomfort sufficient to reduce or affect normal daily activity,
- Severe: inability to work or perform daily activity.

For each AE the causal relationship to the drug will be judged by the investigator as defined below:

- · Probably related,
- Possibly related,
- Not related.

The chronicity of the AE will be classified by the investigator on a 3-item scale as defined below:

- Single occasion: single event with limited duration,
- Intermittent: several episodes of an event, each of limited duration,
- Persistent: event which remained indefinitely.

### Serious adverse events (SAEs)

Serious adverse event is any untoward medical occurrence in a patient or trial subject that at any dose:

- results in death,
- is life-threatening,
- requires inpatient hospitalization or prolongation of existing hospitalization,
- results in persistent or significant disability/incapacity,
- is a congenital anomaly/birth defect, or
- any other important medical event that did not result in any of the outcomes listed above due to medical or surgical intervention but could have been based upon appropriate medical judgement by the investigator.

An elective hospital admission will not be considered as a SAE.

### Suspected unexpected serious adverse reactions (SUSARs)

Unexpected adverse reactions are SUSARs if the following three conditions are met:

- 1. The event must be serious;
- 2. There must be a certain degree of probability that the event is a harmful and an undesirable reaction to the medicinal product under investigation, regardless of the administered dose;
- 3. The adverse reaction must be unexpected, that is to say, the nature and severity of the adverse reaction are not in agreement with the product information as recorded in the reference safety information (RSI, i.e. the IB).

## 2.12.2 Recording of AEs/SAEs/SUSARS

Recording of AEs will be done according to CHDR SOP CGEAE.

## 2.12.3 Reporting of AEs and SAEs

Reporting of SAEs by the investigator to the sponsor

Not applicable, all SAEs will be reported.

List of SAEs which do not require immediate reporting and procedure for reporting

Not Applicable.

## 2.12.4 Follow-up of adverse events

All AEs will be followed until they have abated, returned to baseline status or until a stable situation has been reached. Depending on the event, follow up may require additional tests or medical procedures as indicated, and/or referral to the general physician or a medical specialist. SAEs need to be reported till end of study within the Netherlands, as defined in the protocol.

## 2.12.5 Reporting of SUSARs by the sponsor to the EudraVigilance database

The sponsor will keep detailed records of all AEs which are reported to him/her by the investigator or investigators (CTR: Article 41(3)).

The sponsor will report electronically and without delay to EudraVigilance database all relevant information about any SUSAR (CTR: Article 42).

The period for the reporting of SUSARs by the sponsor to the EMA will take account of the seriousness of the reaction and will be as follows:

- In the case of fatal or life-threatening SUSARs, as soon as possible and in any event not later than **7** days after the sponsor became aware of the reaction (CTR: Article 42(2(a)));
- In the case of non-fatal or non-life-threatening SUSARs, not later than **15 days** after the sponsor became aware of the reaction (CTR: Article 42(2(b)));
- In the case of a SUSARs which was initially considered to be non-fatal or nonlife threatening but which turns out to be fatal or life-threatening, as soon as possible and in any event not later than **7** days after the sponsor became aware of the reaction being fatal or life-threatening (CTR: Article 42(2(c))).

Where necessary to ensure timely reporting, the sponsor may, in accordance with section 2.4 of Annex III, submit an initial incomplete report followed up by a complete report (CTR: Article 42(2)).

#### 2.12.6 Annual safety report

Regarding investigational medicinal products other than placebo, the investigator shall submit annually through CTIS to the Member State concerned a report on the safety of each investigational medicinal product used in a clinical trial (CTR: Article 43).

## 2.12.7 Unblinding procedures for safety reporting

The investigator will only unblind the treatment allocation of a subject in the course of a clinical trial if unblinding is relevant to the safety of the subject (CTR: Annex III 2.5(17)).

When reporting a SUSAR to the EMA, the investigator will only unblind the treatment allocation of the affected subject to whom the SUSAR relates (CTR: Annex III 2.5(18)).

In case of unblinding, describe procedure to maintain blind for persons responsible for the ongoing conduct of the clinical trial such as the management, monitors, investigators) and those persons

responsible for data analysis and interpretation of results at the conclusion of the clinical trial, such as biometrics personnel (CTR: Annex III 2.5(19)).

# 2.12.8 Temporary halt for reasons of subject safety

The sponsor will suspend the study if there is sufficient ground that continuation of the study will jeopardise subject health or safety. The sponsor will submit the notification through CTIS without undue delay of a temporary halt but not later than in 15 days of the date of the temporary halt. It shall include the reasons for such action and specify follow-up measures. The study will be suspended pending a further positive decision by the concerned member state (CTR: Article 38). The investigator will take care that all subjects are kept informed.

# 2.12.9 Urgent safety measures and other relevant safety reporting

Where an unexpected event is likely to seriously affect the benefit-risk balance, the sponsor and the investigator will take appropriate urgent safety measures to protect the subjects. In addition, the sponsor will notify the Member State concerned, through CTIS, of the event and the measures taken. That notification will be made without undue delay but no later than **7 days** from the date the measures have been taken (CTR: Article 54).

## 2.12.10 Data Safety Monitoring Board (DSMB)/Data Monitoring Committee (DMC)

Not applicable.

### 2.13 STATISTICAL ANALYSIS

## 2.13.1 Description of statistical methods

All safety and statistical programming are conducted with SAS 9.4 (maintenance 6) for Windows or newer (SAS Institute Inc., Cary, NC, USA). PK variable programming is conducted with R 4.0.3 for Windows or newer (R Foundation for Statistical Computing/R Development Core Team, Vienna, Austria, 2019).

### 2.13.2 Analysis sets

Data of all subjects participating in the study will be included in the analyses if the data can meaningfully contribute to the objectives of the study.

Safety set

The safety population will be defined as all subjects who were validated (randomised) and received at least 1 dose of study treatment.

Pharmacokinetic analysis set

The PK analysis population is defined as all subjects who were validated (randomised), received at least one dose of study treatment, and have at least one measurable drug concentration in samples collected.

Pharmacodynamic analysis set

The analysis population for pharmacodynamics is defined as all subjects who were validated (randomised), received at least one dose of study treatment, and have at least one post-baseline assessment of the parameter been analysed.

# 2.13.3 Participant demographics and other baseline characteristics

Subject disposition will be listed by subject.

The following subject data will be summarized:

- number and percentage of subjects screened,
- number and percentage of subjects enrolled,
- number and percentage of subjects completed,
- number and percentage of subjects included in safety population.

Demographics and baseline variables

Continuous demographic variables (e.g., age, height, weight, BMI) will be summarized by descriptive statistics (n, mean, SD, median, Min, Max). Qualitative demographic characteristics (sex, race/ethnicity) will be summarized by counts and percentages.

Medical history

Medical history will only be listed.

**Concomitant Medications** 

Previous and concomitant medications will be listed by International Non-proprietary Names, dose, regimen, route and for which indication it was prescribed.

Treatment compliance/exposure

Exposure to study treatment is described in terms of duration of treatment and average infusion rate. The average infusion rate (mL/hr) is summarized by mean, SD, median, Q1, Q3, Min, Max.

## 2.13.4 Randomisation and blinding

Randomization and treatment assignment

Please refer to Subsection 2.10.2.

**Blinding** 

Please refer to Subsection 2.10.2.

Using that data, a sample size calculation was performed. The sample required to achieve a power of at least 80% to detect an expected difference on the cold pressor task (PTT) of 5 seconds (25% of an average score, based on 4 studies, under placebo of 20 seconds) at a two-sided significance level of 0.05, are given in the following Table (Table 6) for a range of within subject CV values:

**Table 8.** Sample size

Within subject CV	Actual power	Sample size
20%	0.796	20
25%	0.845	24
30%	0.825	24

Assuming a within subject CV of 30%, a sample size of 24 would yield a power of over 80% (82.5%) and thus suffices, for the contrast pregabalin - placebo.

#### *Inferential methods*

The study is exploratory, and no formal null hypothesis is set. No adjustments for multiple comparisons will be applied.

## 2.13.6 Planned analysis

#### Pharmacokinetic analysis set

The PK analysis population is defined as all subjects who were validated (randomised), received at least one dose of study treatment, and have at least one measurable drug concentration in samples collected.

## Pharmacodynamic analysis set

The analysis population for pharmacodynamics is defined as all subjects who were validated (randomised), received at least one dose of study treatment, and have at least one post-baseline assessment of the parameter been analysed.

### Subject disposition

Subject disposition will be listed by subject.

The following subject data will be summarized:

- 1. number and percentage of subjects screened,
- 2. number and percentage of subjects enrolled,
- 3. number and percentage of subjects completed,
- 4. number and percentage of subjects included in safety population.

